1.5. Sample Size

The planned sample size for this study is 1050 randomized and treated subjects. These subjects will be allocated into 3 treatment groups in a 1:1:1 ratio. Pair-wise testing of each ALD403 group vs. placebo will be performed. Three hundred and fifty subjects per group provides at least 90% power for the primary endpoint for each comparison assuming a treatment effect of at least 1 day and a common standard deviation of 4 days or less. For the key secondary 75% responder rate endpoints 90% power is achieved for the pair-wise comparisons, assuming a placebo responder rate of 20%, and an ALD403 rate of 31%. These sample size calculations have been performed using Pass 2008 and are based upon a t-test and chi-squared test that should approximate the ANCOVA and CMH tests.³

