2.5. Statistical Assessment of the Trial Objectives

2.5.1. Primary Endpoint

Hypothesis testing will be performed for the primary endpoint: change in frequency of migraine days (Weeks 1-12). This endpoint will be calculated as outlined in Section 2.2.2 and will utilize the missing data rules provided in Section 2.7.2. Summary statistics including confidence intervals for the treatment differences will be used to summarize the results for the primary endpoint. Testing will also be employed. The hypotheses tested are

$$H_0: \Delta_{\text{plb}} = \Delta_{403} \qquad H_a: \Delta_{\text{plb}} \neq \Delta_{403}$$

where Δ_{403} is the change in migraine days for subjects in the ALD403 treatment arm and Δ_{plb} is similarly defined for the placebo subjects. The change from baseline is expected to be negative as migraines are being reduced. While the test outlined above is two sided, as is the alpha level used for this study (i.e. 5%), clinically relevant results require a larger reduction of migraines on the ALD403 arms.

An ANCOVA model will be used to test for a difference between treatment arms. This model will include the change from baseline measure as the response variable. Treatment and variables measuring the stratification factors concepts: baseline migraine days (continuous covariate) and prophylactic medication use (binary covariate: use vs. no use) will be the independent variables.

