2.5.2. Key Secondary Efficacy Analyses

Summary statistics including confidence intervals for the treatment differences will be used to summarize the results for the key secondary endpoints. Testing, as outlined below, will be used for the key secondary endpoints.

Responder Rates

Testing of the 75% migraine responder rate (Weeks 1-4), 75% migraine responder rate (Weeks 1-12) and 50% migraine responder rate (Weeks 1-12) endpoints will be performed with a CMH test controlling for the randomization stratification factors baseline migraine days (<17 days, \geq 17 days) and prophylactic medication use (use vs. no use). Cumulative distribution of the responder rate will be plotted.

Percentage of Subjects with a Migraine on the Day after Dosing

The percent of subjects with a migraine on the day after dosing key secondary endpoint will be tested with a stratified extended CMH test.⁴ Randomization stratification factors baseline migraine days (<17 days, \geq 17 days) and prophylactic medication use (use vs. no use) will be used for this test. An extended CMH test is used here as subjects with missing data will have a value imputed between 0 and 1 as outlined in Section 2.7.2.

Reduction in Migraine Prevalence from Baseline to Week 4

The reduction in migraine prevalence from baseline to Week 4 endpoint will be the difference in daily prevalence rates between Week 1 and baseline, Week 2 and baseline, etc. The treatment effect will be tested using a repeated-measures approach (Mallinckrodt and Lipkovich, 2016),⁵

using the subject level change in migraine rate (see Section 2.2.2) for Weeks 1, 2, 3 and 4 as the outcome variable. The model will specify an unstructured variance/covariance matrix and include the treatment group, week, baseline value of the outcome variable and with treatment group-by-week interaction. The Kenward-Roger approximation will be used to estimate the degrees of freedom.

Headache Impact Test (HIT-6)

The change in HIT-6 total score will be tested using an ANCOVA model similar to the one used for the primary endpoint. This model will include the HIT-6 change from baseline at Week 12 as the response variable. Treatment and the stratification factors will be the independent variables.

Acute Migraine Medication Usage

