where W is the number of days the diary was completed/20, X_c is the available average daily results for the current interval and X_p are the average imputed daily results for the previous interval.

Missing Data Rule for Prevalence Endpoints.

For the percentage (prevalence) of subjects with a migraine on the day after dosing and reduction in migraine prevalence from baseline to Week 4 endpoints subjects who did not complete the eDiary on any day following dosing will be included in the calculation based upon their Week 1-4 daily migraine rate. Hence, subjects with a migraine on a given day will have a rate of 1 for that day, subjects who completed the eDiary and did not have a migraine will be included as a 0, and subjects who did not complete the eDiary will be included with a value between 0 and 1 equal to their prevalence rate in Weeks 1-4 (i.e. the number of Weeks 1-4 migraine days divided by 28).

Missing Data Rule for HIT-6

If a subject does not complete the HIT-6 at week 12 their Week 12 change from baseline result will be set to imputed values using LOCF. This imputation will only be performed at Week 12.

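### The confirmatory HIT-6 test, as written, leaves out baseline HIT-6 (a loss of precision, not a bias), and no sensitivity analysis covers its LOCF rule

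*SAP*

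**What the plan says.** SAP 2.3 puts HIT-6 among the eight confirmatory endpoints. In SAP Table 2 it appears only for 300 mg, in Key Secondary #5, the last step. It shares that step with acute medication usage at Holm thresholds 0.025 and 0.05.

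SAP 2.5.2 describes the test as an ANCOVA resembling the primary one: "This model will include the HIT-6 change from baseline at Week 12 as the response variable". It continues: "Treatment and the stratification factors will be the independent variables". Baseline HIT-6 is not in that list. The text also does not say whether migraine days enter as a continuous variable, as in the primary model in SAP 2.5.1, or as the <17 / ≥17 stratum.

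SAP 2.7.2 covers a subject who does not complete HIT-6 at Week 12: "their Week 12 change from baseline result will be set to imputed values using LOCF". The rule applies only at Week 12. SAP 2.2.2 makes the total score missing if any one item is missing.

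The schedule of events, the same in both documents, has HIT-6 at Screening, Day 0, Weeks 4, 12, 16 and 24, and Week 32 or early termination. There is none at Week 8. The missing-data and baseline sensitivity analyses in SAP 2.7.3 all concern migraine days.

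**The concern.** Two other confirmatory models in the SAP adjust for the baseline of their own outcome. The primary ANCOVA includes baseline migraine days, and the prevalence model in SAP 2.5.2 includes the baseline value of the outcome. The HIT-6 model analyses a change score without the corresponding term, although a pre-dose HIT-6 is taken on Day 0. At stake is power that costs nothing to obtain.

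The second issue is the missing-data rule. Carrying a score forward assumes that it would not have moved up to Week 12. If scores move between Weeks 4 and 12, or if subjects who miss Week 12 differ from those who attend, the treatment contrast can shift, above all when the arms lose different proportions of subjects. The SAP tests the robustness of the primary endpoint to its missing-data rule but does nothing comparable for HIT-6.

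**Working it through.** **Plan's own figure.** The only power statements are in SAP 1.5, and none concerns HIT-6. For the primary endpoint the SAP states "at least 90% power for the primary endpoint for each comparison assuming a treatment effect of at least 1 day". The SD behind that figure is at most 4 days. With 350 per arm and two-sided 5%:
- 1 / (4 × √(2/350)) = 1 / 0.3024 = 3.307, and 3.307 − 1.960 = 1.347, so power is 91.1%. The statement reproduces.
- The responder comparison (20% vs 31%) gives 91.8%, so it also reproduces.

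The documents give no HIT-6 effect, SD, correlation or missing rate. Every HIT-6 input below is therefore an assumption, shown over a range.

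**1. Cost of omitting baseline HIT-6.** Let r be the baseline-to-Week 12 correlation and k the baseline SD divided by the Week 12 SD. The variance with adjustment, relative to the unadjusted change score, is (1 − r²) / (1 + k² − 2rk). With k = 1 this reduces to (1 + r)/2.

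| r | k = 1 | k = 0.7 |
|---|---|---|
| 0.3 | 0.65 | 0.91/1.07 = 0.85 |
| 0.5 | 0.75 | 0.75/0.79 = 0.95 |
| 0.7 | 0.85 | 0.51/0.51 = 1.00 |

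- With k = 1 the SE is multiplied by 0.81, 0.87 and 0.92. Put the other way, omission inflates the SE by about 8% to 24% (1/0.92 to 1/0.81).
- A test with 80% power without the covariate (1.960 + 0.842 = 2.802) rises to 93.5%, 89.9% and 86.0%. For r = 0.3: 2.802/0.806 − 1.960 = 1.52, which gives 93.5%.
- If baseline migraine days are already in the model, with an assumed correlation of 0.3 with baseline HIT-6, the SE factors are 0.82, 0.88 and 0.93 (at r = 0.3, 0.5 and 0.7). Little of the gain is lost.
- With k = 0.7 the gain shrinks and disappears at r = 0.7.

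**2. LOCF with equal missingness.** If a fraction m in each arm is missing at random with respect to outcome, the expected contrast is (1 − m)·d12 + m·d4, where d4 and d12 are the Week 4 and Week 12 effects. The shift is m·(d4 − d12). For m from 3% to 20% and effects that differ by up to 1 point, the shift is at most 0.03 to 0.20 point. The scale runs from 36 to 78.

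A drift common to both arms cancels. With 8% missing and a 2-point drift, each arm mean moves by 0.08 × 2 = 0.16 point, and the difference between arms moves by 0.

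**3. LOCF with unequal missingness.** With no true effect and a common drift g from Week 4 to Week 12, the bias is −(mA − mP)·g, where mA and mP are the missing fractions on active drug and placebo. With 10% vs 20% missing and g = −2 (improvement), the bias is −(−0.10)(−2) = −0.20 point, in favor of the drug.

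**4. Simulation.** There were 2000 runs with 350 per arm. The main setting has SD 6, pairwise correlations of 0.5, 0.45 and 0.65, and missingness that depends on the Week 4 change. The comparator is a two-visit repeated-measures model with baseline HIT-6. It is close to the SAP's prevalence model but adds stratification and baseline-by-visit terms.
- 10% missing in each arm, effect −1 at Week 4 and −1.5 at Week 12: LOCF without baseline gave −1.48 (SE 0.48, power 86%). LOCF with baseline had SE 0.41. Repeated measures gave −1.50 (SE 0.42, power 95%).
- 15% missing in each arm, no effect: LOCF without baseline rejected in 5.4% of runs, repeated measures in 5.7%.
- 5% vs 10% missing, no effect: LOCF bias was −0.11 point with type I error 5.9%. Repeated measures rejected in 6.1%.
- 10% vs 20% missing, no effect, three sets of the remaining assumptions: LOCF bias was −0.12 to −0.42 point with type I error 5.2% to 12.7%. Repeated measures had bias near 0 and type I error 4.0% to 5.6%.

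This simulated missingness is of the kind under which repeated measures is valid, so it favors that model by design.

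**The case against.** Four objections carry weight.

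- **Wording.** SAP 2.5.2 calls the HIT-6 model similar to the primary one, and the primary model adjusts for its own outcome's baseline. The sponsor may have meant to include baseline HIT-6. The sentence that lists the variables does not say so, so the text needs settling on either reading.
- **What is carried.** A reader might infer that LOCF always copies an 8-week-old Week 4 score. The documents do not support that. Withdrawing subjects are asked to attend an early-termination visit (Protocol 8.4.4), at which HIT-6 is scheduled. By SAP Table 3, a score from Days 71 to 98 is itself the Week 12 value, and one from Days 43 to 70 is more recent than Week 4.
- **Alternative model.** A reader might also infer that the SAP already provides a repeated-measures analysis for HIT-6. It does not. Those models serve migraine prevalence and the primary endpoint's sensitivity analyses, and the prevalence model has no prophylactic-use term. Making repeated measures the main HIT-6 test would exchange one untestable assumption for another.
- **Consequence.** HIT-6 is reached only after 12 earlier tests succeed (1 + 3 + 2 + 1 + 3 + 2), and no later claim depends on it. Follow-up continues after treatment stops (Protocol 8.4.1) and staff check questionnaires for completeness (Protocol 10.2.6), which limits missing data.

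These points stand. They narrow the concern, but they do not supply the missing covariate or the missing sensitivity analysis.

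**Conclusion.** The point holds at modest size. As written, the model omits baseline HIT-6. Under equal SDs and r of 0.3 to 0.7, adjustment would multiply the variance by 0.65 to 0.85. If baseline scores are narrower than Week 12 scores, the gain is smaller and may vanish. The omission does not bias the randomized comparison.

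LOCF has little effect on the contrast when missingness is equal: at most about 0.2 point with up to 20% missing and a 1-point difference between the Week 4 and Week 12 effects. It can favor the drug when placebo loses more subjects; the larger figures rest on an assumed 10% vs 20% imbalance that nothing in the documents predicts.

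A reader might infer that LOCF materially understates the SE here. The calculations do not show this: type I error was 5.4% under equal missingness, and the SE with baseline was 0.41 against 0.42 for repeated measures. Most of the power gain comes from the covariate, which a plain ANCOVA can carry.

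**What to change.** In SAP 2.5.2, name baseline HIT-6 as a continuous covariate in the HIT-6 ANCOVA, alongside baseline migraine days and prophylactic use, and state the form in which migraine days enter. In SAP 2.7.2, say what is done for a subject with no post-baseline score, and whether an early-termination score may be carried.

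In SAP 2.7.3, add a repeated-measures analysis of the Week 4 and Week 12 HIT-6 change, at least as a sensitivity analysis. It should have baseline HIT-6, treatment, visit and treatment-by-visit, an unstructured covariance, Kenward-Roger degrees of freedom and no LOCF.

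This needs no new data, only SAP wording and slightly more analysis work, and should be settled before sponsor representatives are unblinded for the Week 12 analysis (SAP 1.4). The drawback is that the repeated-measures result relies on data being missing at random, which is a reason to read it beside the LOCF result.

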2.7.3. Sensitivity Analyses

A number of sensitivity analyses will be performed. The first group of sensitivity analyses will look at the missing data rules as outlined below.

1. The primary endpoint will be analyzed using a modification to Missing Date Rule 2 to better understand the robustness of the selected algorithm. The analysis replaces X_p with X_b , where X_b are the baseline average daily results, if the subject withdrew from the study due to an adverse event, study burden, lack of efficacy or worsening of study indication or if the subject died.
2. The primary endpoint will be analyzed using repeated measures where the individual time periods (Weeks 1-4, 5-8 and 9-12) are included in the model and Missing Date Rule 2 is not used. Hence, subject who do not complete the diary for more than 7 days out of 28 are not included for that 4 week period. The model will specify an unstructured variance/covariance matrix and include the treatment group, timepoint, baseline, and treatment group-by-timepoint interaction. The Kenward-Roger approximation will be used to estimate the degrees of freedom.

The second group of sensitivity analyses change the definition of baseline. Baseline will be redefined using 28-days of headache diary data ending on the day of the first dose. The primary analysis will be repeated using this updated definition of the baseline.

Finally, a repeated measures model will be run that includes all 6 four week intervals and both missing data rules outlined in Section 2.7.2. This model will be identical in structure to the model specified for the missing data sensitivity analysis outlined above but will look at how the primary analysis, based upon the ANCOVA model, compares to a repeated measures analysis.

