Compute p-values key secondary endpoints #3 and follow Holm's testing procedure, see [Table 2](#) for the P-value comparisons. If all endpoints are statistically significant, then go to step 6 below. Otherwise stop.

Compute p-values key secondary endpoints #4 and follow Holm's testing procedure, see [Table 2](#) for the P-value comparisons. If all endpoints are statistically significant, then go to step 7 below. Otherwise stop.

Compute p-values key secondary endpoints #5 and follow Holm's testing procedure, see [Table 2](#) for the P-value comparisons. If all endpoints are met statistically, then declare statistical significance. Otherwise stop.

All other efficacy analyses and associated p-values will be deemed exploratory and no adjustment for multiplicity will be used.

Table 2: Key Efficacy Analyses and Multiplicity Adjustment

Testing Sequence	Endpoint	Population	Declare Significant
Key Secondary #1	300 mg Wk1-4 75% responder rate	FAP	$p_{(1)} < 0.0167$
	300 mg Wk1-12 75% responder rate	FAP	$p_{(2)} < 0.025$
	300 mg % subjects with migraine on the day after dosing	FAP	$p_{(3)} < 0.05$
Key Secondary #2	300 mg migraine prevalence Day 1-28 Post dose	FAP	$p_{(1)} < 0.025$
	300 mg wk 1-12 50% responder rate	FAP	$p_{(2)} < 0.05$
Key Secondary #3	100 mg Wk1-4 75% responder rate	FAP	$p_{(1)} < 0.0167$
	100 mg Wk1-12 50% responder rate	FAP	$p_{(2)} < 0.025$
	100 mg % subjects with migraine on the day after dosing	FAP	$p_{(3)} < 0.05$
Key Secondary #4	100 mg migraine prevalence Day 1-28 Post dose	FAP	$p_{(1)} < 0.025$
	100 mg wk 1-12 75% responder rate	FAP	$p_{(2)} < 0.05$
Key Secondary #5	300 mg Acute medication usage	FAP	$p_{(1)} < 0.025$
	300 mg Change from baseline in HIT-6	FAP	$p_{(2)} < 0.05$

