2.4. Trial Day

Trial endpoints will be reported within analysis windows or analysis intervals based upon the actual date of the assessment. Assignment of results to these time points is based upon the trial day. Trial day is defined as:

$$\text{Trial day} = \text{date of assessment} - \text{date of treatment}$$

Analysis Windows used to report non-diary endpoints are outlined in [Table 3](#).

Table 3: Analysis Windows

Visit	Range	Target Day	If more than one which one is used for analyses
Screening	< Day 0		First value
Day 0	Day 0 to Day 9	Day 0	Closest to Target Day
Week 2	Day 10 to Day 21	Day 14	Closest to Target Day
Week 4	Day 22 to Day 42	Day 28	Closest to Target Day
Week 8	Day 43 to Day 70	Day 56	Closest to Target Day
Week 12	Day 71 to Day 98	Day 84	Closest to Target Day
Week 16	Day 99 to Day 126	Day 112	Closest to Target Day
Week 20	Day 127 to Day 154	Day 140	Closest to Target Day
Week 24	Day 155 to Day 203	Day 168	Closest to Target Day
Week 32	> Day 204	Day 224	Closest to Target Day

Note: If two observations exist with same distance to target day, use first observation.

For the eDiary data used to produce the migraine and headache endpoints the intervals specified in Table 4 will be used to collapse the daily data into 4, 12, and 24 week intervals. For these data baseline is defined as the 28 days starting on the day of the first diary entry.

Table 4: eDiary Headache/Migraine Endpoint Analysis Intervals

Diary Weeks	Trial Time	Comments	Endpoints
Baseline	The 28 days starting from the first eDiary entry		All eDiary related endpoints
1-4	Days: 0-27	Day 0 = First day of treatment	All eDiary related endpoints
5-8	Days: 28-55		All eDiary related endpoints
9-12	Days: 56-83		All eDiary related endpoints
1-12	Weeks 1-4, 5-8, and 9-12	Average of the 4 week intervals after imputation methods are applied	All Primary and Secondary eDiary related endpoints
13-16	Days: 84-111		All eDiary related endpoints
17-20	Days: 112-139		All eDiary related endpoints
21-24	Days: 140-167		All eDiary related endpoints
13-24	Weeks 13-16, 17-20 and 21-24	Average of the 4 week intervals after imputation methods are applied	All Primary and Secondary eDiary related endpoints
1-24	Weeks 1-4, 5-8, 9-12, 13-16, 17-20 and 21-24	Average of the 4 week intervals after imputation methods are applied	All Primary and Secondary eDiary related endpoints

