3.4.2.1. Percentage of Subjects with a Migraine on the Day after Dosing

The percentage of subjects with a migraine will be summarized for each treatment group at baseline and each day from Day 0 to Day 7. A p-value for the difference from Placebo in the percentage of subjects with a migraine on the day after dosing (Day 1) will be provided. The average number of migraine hours on each of these days will also be presented.

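### The baseline sensitivity analysis counts Day 0 in both baseline and outcome, and SAP Tables 2 and 4 give the gated migraine prevalence endpoint different windows

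*SAP*

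**What the plan says.** **Sensitivity baseline.** SAP 2.7.3 repeats the primary analysis with a different baseline: "Baseline will be redefined using 28-days of headache diary data ending on the day of the first dose". The outcome intervals are left unchanged. SAP 2.4, Table 4, notes "Day 0 = First day of treatment" and assigns Days 0-27 to Weeks 1-4. The primary baseline in the same table is "The 28 days starting from the first eDiary entry".

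**Schedule.** Protocol 10.3 starts the 28-day diary period on the day the eDiary is handed out at screening. SAP 1.2 puts randomization 28-30 days after screening and Day 0 up to 8 days after that. On timing within those 8 days, SAP Table 1 footnote 2 prefers the randomization day itself where feasible. Footnote 2 of the schedule in Protocol Section 2 gives only the 8-day limit.

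**Prevalence endpoint.** SAP 2.3, Table 2, lists "300 mg migraine prevalence Day 1-28 Post dose" in Key Secondary #2 and "100 mg migraine prevalence Day 1-28 Post dose" in Key Secondary #4. Table 4 applies Days 0-27 to every eDiary endpoint in Weeks 1-4. SAP 3.4.2.1 fixes the numbering: "subjects with a migraine on the day after dosing (Day 1) will be provided". SAP 2.2.2 and Protocol 13.4.2 define each weekly rate as that week's migraine days over 7, without saying which days make up the week. The missing-data rule in SAP 2.7.2 covers "subjects who did not complete the eDiary on any day following dosing" and imputes from "the number of Weeks 1-4 migraine days divided by 28".

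**The concern.** The alternative-baseline analysis exists to show whether the primary result depends on which 28 days serve as baseline. If the new window includes the infusion day, the covariate contains a value that treatment may already have affected, and the same day is counted again in the outcome. For a subject who starts the diary at screening and is randomized and dosed 28 days later, that day is the only one the analysis adds.

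The prevalence mismatch concerns a confirmatory test. At 300 mg, both endpoints in Key Secondary #2 must be significant before the 100 mg primary comparison is reached. Two programmers working from the same SAP could build the weekly counts from different days.

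**Working it through.** **Plan's own figure.** The 1-day effect used below for scale comes from SAP 1.5 (350 per arm, SD 4, two-sided 5%). Its standardized value is 1 / (4 × √(2/350)) = 3.307, and power is Φ(3.307 - 1.960) = 0.911. This agrees with the stated 90% or more. Nothing in this point changes it.

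**Day windows.** Let S be the screening day, with the diary started on S, so Day 0 lies between S+28 and S+38. The primary baseline is S to S+27.

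| Day 0 | Primary baseline | Days added by Days -27 to 0 | Days added by Days -28 to -1 |
|---|---|---|---|
| S+28 | Days -28 to -1 | 1 (Day 0 only) | 0 |
| S+30 | Days -30 to -3 | 3 | 2 |
| S+38 | Days -38 to -11 | 11 | 10 |

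Days -27 to 0 and Days 0-27 share exactly one day, Day 0. Days -28 to -1 share none.

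**Effect on the estimate.** A Day 0 migraine adds 1 to the redefined baseline and 1 to the Weeks 1-4 count. It contributes 0 to the Weeks 1-4 change and 1/3 - 1 = -0.67 to the Weeks 1-12 change. ANCOVA then adjusts for baseline. Let b be the slope of the outcome level on baseline and d the Day 0 migraine risk, active minus placebo. Moving Day 0 into the baseline shifts the treatment estimate by -b × d. A beneficial treatment estimate is negative, so:

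- d < 0 (drug helps on Day 0): the shift is positive, toward zero.
- d > 0 (drug worsens Day 0): the shift is negative, away from zero.
- d = 0: no shift.

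The documents give neither b nor d, so the sizes are assumptions:

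- 1-day effect spread evenly over 28 days, |d| = 1/28 = 0.036: shift 0.5 × 0.036 = 0.018 day at b = 0.5, and 0.036 day at b = 1.
- |d| between 0 and 0.20 with b = 1: shift 0 to 0.20 day.

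**Diary completeness in a Day -28 to -1 window.** Eligibility allows at most 4 missed days in a 28-day qualifying window. If Day 0 falls m days after the first day following that window, the new window keeps 28 - m of its days, so at least 24 - m are completed. Missing Data Rule 1 needs 21, so it is guaranteed only for m ≤ 3.

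- Protocol 8.1, item 10, counts the 28 days before randomization. Then m is the number of days from randomization to dosing, and the guarantee holds up to 3.
- The Protocol synopsis counts the 28-day screening period. With randomization at S+30, m is that number plus 2, and the guarantee holds only up to 1.

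Rule 2 cannot fill the gap, because it borrows from a previous interval and baseline has none.

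**Prevalence.** Days 0-27 and Days 1-28 share 27 days. Day 0 is only in the first; Day 28 is only in the second, and Table 4 assigns Day 28 to Weeks 5-8. The four-week average effects differ by (effect on Day 28 - effect on Day 0) / 28. If the effect is constant from Day 0, they are equal. If Day 0 carries no effect and all later days the same one, Days 0-27 captures 6/7 (86%) of the Week 1 effect and 27/28 (96%) of the four-week average.

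**The case against.** The strongest reply is about scale and natural reading. One day in 28 is shared, in an analysis that is not part of the testing sequence. Ending on the dosing day may have been meant as ending at the dose. For prevalence, Table 4 explicitly governs the eDiary endpoints, imputation uses the Weeks 1-4 count, and Table 2 is a list of thresholds with short row names. Consecutive seven-day blocks of Days 0-27 are the obvious reading, and the wording about days after dosing also serves the day-after-dosing endpoint, so it is weak support for Days 1-28.

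The point about scale stands and sets the severity. The rest stands only in part. No rule divides Day 0 at the infusion, whereas SAP 3.2 does require non-diary baselines to precede administration. Table 2's Day 1 cannot be the dosing day under the SAP's own numbering. A gated endpoint should not depend on which table a programmer consults first.

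A reader might infer three stronger things that the documents do not support:

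- *The overlap can only dilute the effect.* The direction follows the sign of the Day 0 difference. Protocol 5.4 lists headache among the common adverse events under ALD403 or placebo, without splitting by arm or day, so neither direction is established.
- *The primary result or type I error is compromised.* With the diary started at screening, the primary baseline ends on Day -1 at the latest. A first entry one day late with dosing at S+28 would bring Day 0 into it, but Protocol 10.3 starts the diary on the day it is handed out, and nothing shows that this departure is expected.
- *The prevalence mismatch changes a test result.* Nothing in the documents shows that it would.

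**Conclusion.** Both parts hold, and both are minor. Read literally, the alternative baseline shares Day 0 with Weeks 1-4, and the SAP states two windows for the prevalence endpoint with no weekly day ranges.

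The baseline shift is zero without a Day 0 difference and 0.018 to 0.036 day if a 1-day effect is spread evenly with slope 0.5 to 1. It could reach 0.20 day under the largest assumed Day 0 risk difference with slope 1. These sizes rest entirely on assumed slopes and Day 0 effects; the overlap itself does not. The consequence is confined to one sensitivity analysis. The prevalence mismatch is an ambiguity to settle in a confirmatory endpoint, not a demonstrated error in its result.

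**What to change.** 1. In SAP 2.7.3, end the redefined baseline on the day before the first dose (Days -28 to -1) and apply Missing Data Rule 1. Add a fallback for fewer than 21 completed days, for example keeping the primary baseline. The cost is one phrase and one sentence. One limit should be acknowledged: for subjects dosed soon after screening, this window nearly repeats the primary baseline (0 added days at S+28, 2 at S+30), so the analysis is informative mainly through subjects dosed later.
2. Before the Week 12 unblinding described in SAP 1.4, confirm the intended prevalence window, use it in both tables and state the four weekly ranges. Days 0-27 (0-6, 7-13, 14-20, 21-27) agrees with Table 4 and with the Weeks 1-4 rate used for imputation, and needs two row labels changed in Table 2. Days 1-28 (1-7, 8-14, 15-21, 22-28) would need its own row in Table 4.
3. Reconcile the Protocol and SAP footnotes on the timing of the first dose after randomization. This point takes no side on which is intended.

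None of this changes the data collected or the primary analysis.
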